#### **4. POPULATIONS FOR ANALYSES**

In this study 3 populations for analyses are defined: Treated Set, Evaluable Set, and PK Set.

Furthermore, any additional exploratory analysis not identified in the SAP will be identified in the final CSR as exploratory post hoc analyses, including analyses for additional study populations or subgroups of interest.

##### **4.1 Population Descriptions**

###### **4.1.1 Treated Set**

All subjects who received at least one dose of study drug (FLX475 or pembrolizumab). All demographics, Baseline characteristics, efficacy and safety data will be analyzed using the Treated Set as a primary analysis population.

###### **4.1.2 Tumor Evaluable Set**

All subjects who are enrolled, complete at least one cycle of investigational drug, and is evaluable for tumor response based on RECIST, version 1.1. Tumor Evaluable Set will be used for supportive summaries of efficacy data that related to tumor response.

###### **4.1.3 PK Set**

All subjects who received at least one dose of FLX475, and have at least one quantifiable plasma concentrations of FLX475.

PK set will be determined after database lock by the study pharmacometrist and confirmed by Sponsor.

The PK set will be used for all PK concentration data for this study which include concentrations listings, concentrations summary and concentration-time profiles along with plasma PK analysis, the PK parameters listings and summaries, graphical presentation of all PK parameters data if applicable, and statistical analysis of PK parameters if applicable.

## **5. PARTICIPANT DISPOSITION AND ANALYSIS POPULATIONS**

Subject disposition and analysis population analysis will be based on all screened subjects and all enrolled subjects, respectively. Subject disposition and analysis populations will be summarized descriptively as described in section 3.1 (categorical descriptive analysis).

### **5.1.1 Subject Disposition**

Subject disposition will include the number of subjects who was screened, the number of subjects who was enrolled, the number of subjects who completed the study as planned, subjects withdrawn from the study, as well as the primary reason for termination and the primary reason for end of treatment. Subject disposition will be summarized descriptively.

### **5.1.2 Analysis Populations**

The number of subjects included in each study populations will be summarized descriptively, as well as the reason for exclusion.

## **6. PROTOCOL DEVIATIONS**

Protocol deviations will be presented for each subject in the by-subject data listings.

Prior to database lock, all protocol deviations will be reviewed by medical monitors and sponsor.

Protocol deviations (minor) and important protocol deviations (major) will be categorized.

Protocol deviations are tracked within [REDACTED] Clinical Trial Management System (CTMS).

## 7. DEMOGRAPHIC AND BASELINE INFORMATION

Demographic and baseline information analysis will be based on the treated set. Demographic and baseline information will be summarized descriptively as described in section 3.1.

### 7.1 Demographics

The following demographic parameters will be analyzed:

#### Continuous descriptive analysis:

- Age (years)
- Baseline Height (cm)
- Baseline Weight (kg)
- Baseline BMI (kg/m^2)

#### Categorical descriptive analysis:

- Sex
- Childbearing Potential
- Race

### 7.2 Medical History

Medical / Surgical history will be coded using MedDRA® and will be presented in the by-subject data listings.

### 7.3 Oncology History

Oncology history information, including prior cancer disease, current cancer diagnosis, treatment of cancer with systemic cancer therapy/radiotherapy/surgery and best overall response, will be presented in the by-subject data listings. Prior cancer disease will be summarized descriptively as described in section 3.1, as well as current cancer diagnosis and previous cancer treatment.

[REDACTED]

[REDACTED]

[REDACTED]

[REDACTED]

**8. TREATMENT EXPOSURE**

Study drug administration results will be presented using the treated set, as well as the data of dose modification. Study drugs include FLX475 and Pembrolizumab.

A by-subject data listing will be generated for study drug administration of FLX475 and will include study drug administration date, time, planned daily dose, and actual daily dose. For Pembrolizumab, this listing will include date of infusion, start time, stop time, planned dose, and actual dose administered.

Treatment exposure will be summarized by cohort for FLX475 and Pembrolizumab. Measures of extent of exposure include the total number of cycles per subject, total cumulative dose per subject, and duration of exposure (days). Dose modification will be summarized as well.

The summary of treatment exposure will also include Relative Dose Intensity (%), which will be calculated as

$$(\text{Actual Dose} / \text{Planned Dose at study start}) \times 100.$$

For more information, contact the Office of the Vice President for Research and Economic Development at [contact] or [[contact]](mailto:[contact]).

■  

A large black rectangular redaction box covers the bottom half of the page. At the top, there are several smaller black redaction boxes of varying sizes and positions, including a cluster on the left side and a single box on the right side.

**11. PHARMACODYNAMICS**

Not applicable.

---

[REDACTED]

[REDACTED]

[REDACTED]

## 12. EFFICACY

Efficacy endpoints will be analyzed for the treated set and tumor evaluable set using all tumor assessment results from baseline until the disease progression confirmation or last evaluable tumor assessment before such as start of new anticancer therapy, death, lost to follow-up, etc. Efficacy endpoints will be summarized descriptively as described in Section 3.1 and analyzed as described in Section 3.3.

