Subjects may continue to receive study therapy until the earliest of the following: subject withdrawal from study, confirmed progression of cancer, intolerable study-drug-related toxicity despite appropriate dose modification, the development of intercurrent illness that precludes continued study therapy, pregnancy or breastfeeding, substantial noncompliance with study procedures, completion of Treatment Phase comprising up to 35 treatment cycles for FLX475 and an approximate of 2 years' treatment (35 doses) for pembrolizumab, or study discontinuation.

Criteria for Evaluation:

Efficacy will be assessed according to the RECIST version 1.1 and iRECIST

Safety and tolerability will be assessed using CTCAE version 5.0

Primary Endpoint:

- Objective Response Rate (ORR) by RECIST 1.1

Secondary Endpoints:

- Efficacy in accordance with RECIST 1.1: DCR, TTR, DOR, PFS
- Efficacy in accordance with iRECIST: iORR, iDCR, iTTR, iDOR, iPFS
- Efficacy: OS
- Safety and tolerability: AEs, Laboratory assessments (including hematology, biochemistry, coagulation, urinalysis, vital signs, physical examination, ECG and ECOG)

Statistical Methods:

Treated Set will include all subjects who received at least one dose of study drug (FLX475 or pembrolizumab). All demographics, Baseline characteristics, efficacy and safety data will be analyzed using the Treated Set as a primary analysis population. Tumor Evaluable Set will include all subject

who are enrolled, complete at least one cycle of investigational drug, and is evaluable for tumor response based on RECIST, version 1.1, and will be used for supportive efficacy analysis.

In general, all data will be summarized with descriptive statistics (number of subjects, mean, standard deviation, minimum, median and maximum) for continuous endpoints, and frequency and percentage for categorical endpoints unless other specified. As each cohort will enroll target subjects separately and so the analyses will be performed separately by cohort as well. The data summaries will be presented by stage and overall across stages for each cohort.

Efficacy analysis will be conducted based on Treated Set and Tumor Evaluable Set. Tumor-related endpoints will be analyzed based on investigator's assessment using RECIST version 1.1, and the result from assessment using iRECIST also be presented.

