11.4.2. Efficacy Analysis

Efficacy analysis will be conducted based on Treated Set and Tumor Evaluable Set. Tumor-related endpoints will be analyzed based on investigator's assessment using RECIST version 1.1, and the result from assessment using iRECIST also be presented.

The primary efficacy endpoint is Objective Response Rate (ORR) defined as the proportion of subjects whose confirmed best overall response is either Complete Response (CR) or Partial Response (PR) according to RECIST version 1.1. The best overall response is the best response recorded from the treatment start date until the earliest of disease progression or last evaluable tumor assessment before events such as start of new anticancer therapy, death, lost to follow-up, etc.

The DCR is defined as the proportion of subjects with confirmed best overall response of CR, PR or SD according to RECIST version 1.1.

The ORR and DCR will be presented with exact 95% Confidence Interval (CI) using the Clopper-Pearson method. Based on the cumulative data about ORR along with prior assumption at each stage, posterior probability of ORR $\geq 15\%$ for cohort 1 and ORR $\geq 30\%$ for cohort 2 would be computed to determine go/no-go decision of the next stage. This cumulative data analysis will be implemented only if at least one response is observed from stage 1 of each cohort.

Time-to-event endpoints, including TTR, DoR, PFS and OS, will be summarized descriptively and graphically using Kaplan-Meier (KM) methodology. Median KM estimates and 95% CI will be presented. For the tumor-related time-to-event endpoints, subjects who have not experience any event (Progressive Disease (PD) or Death) at the time of analysis will be censored at the date of the last evaluable tumor assessment. However, if the subject progresses or dies after two or more consecutive missed assessments or start of new anticancer therapy, the subject will be censored at the time of the last evaluable assessment prior to starting new anti-cancer therapy/missed assessments. If the subject has no evaluable baseline/post-baseline assessment, subject will be censored at the date of first administration of study treatment.

TTR is defined as the time from the date of first administration of study treatment to first documented CR or PR.

DoR is measured from the date of the first observation of tumor response (CR or PR, whichever occurs first) to the date of disease progression or death for the subject with an objected response.

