### 12.2 Time to Event Endpoints (TTR, DoR, PFS and OS)

The time to event endpoints, including time to response (TTR), duration of response (DoR), progression-free survival (PFS) and overall survival (OS) will be summarized descriptively and graphically by the Kaplan-Meier methodology, as described in Section 3.3.

TTR is defined as the time from the date of first administration of study treatment to first documented CR or PR. DoR is measured from the date of the first observation of tumor response (CR or PR, whichever occurs first) to the date of disease progression or death for the subject with an objective response. PFS is defined as the time from the date of first administration of study treatment to determination of tumor progression by RECIST version 1.1 or death due to any cause, whichever occurs first. OS is defined as the duration of time from the treatment start date to time to death from any cause. If subjects survive at the time of analysis, the subject will be censored at the last date of survival confirmed.

TTR, DoR, PFS, and OS will be calculated in days, as well as in months.

For the tumor-related time-to-event endpoints, subjects who have not experience any event (Progressive Disease (PD) or Death) at the time of analysis will be censored at the date of the last evaluable tumor assessment. However, if the subject progresses or dies after two or more consecutive missed assessments

or start of new anticancer therapy, the subject will be censored at the time of the last evaluable assessment prior to starting new anti-cancer therapy/missed assessments. If the subject has no evaluable baseline/post-baseline assessment, subject will be censored at the date of first administration of study treatment. In case of subjects entering the extension part, the data will be treated as censored at the date of the last evaluable tumor assessment on or before the first administration date in the extension part.

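### SAP 12, Protocol 11.4.2 and the synopsis let OS and PFS be run in the Tumor Evaluable Set, against SAP 4.1.2 and Protocol 11.2; an OS curve there would carry at least about three weeks of guaranteed survival

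*SAP*

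**What the plan says.** Three places apply both analysis sets to efficacy without naming an exception.

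- SAP 12: "Efficacy endpoints will be analyzed for the treated set and tumor evaluable set using all tumor assessment results from baseline". The section then refers to SAP 3.3 for the method, and SAP 3.3 contains only Kaplan-Meier analysis of time-to-event endpoints.
- Protocol 11.4.2: "Efficacy analysis will be conducted based on Treated Set and Tumor Evaluable Set". PFS and OS are defined later in that section.
- Protocol synopsis: it repeats the both-sets rule and says the Tumor Evaluable Set "will be used for supportive efficacy analysis".

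OS is listed among the secondary efficacy endpoints in SAP 2.3.2.

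Two places are narrower. SAP 4.1.2 says: "Tumor Evaluable Set will be used for supportive summaries of efficacy data that related to tumor response". Protocol 11.2 has the same restriction. SAP 4.1.1 makes the other set primary: "efficacy and safety data will be analyzed using the Treated Set as a primary analysis population".

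To enter the Tumor Evaluable Set a subject must "complete at least one cycle of investigational drug, and is evaluable for tumor response based on RECIST, version 1.1". Neither document defines evaluable. Both clocks start at first dose. For OS: "OS is defined as the duration of time from the treatment start date to time to death from any cause". For PFS: "PFS is defined as the time from the date of first administration of study treatment to determination of tumor progression by RECIST version 1.1"; a death from any cause also counts as an event. SAP 12.2 also censors, at first dose, a subject with no evaluable baseline or post-baseline assessment. It makes no exception for a subject who has died.

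**The concern.** Membership of the Tumor Evaluable Set is decided by what happens after first dose, but OS is counted from first dose. A subject who dies in the first cycle cannot enter the set, while everyone who does enter keeps the weeks they had to survive to qualify. This is immortal-time bias. The visible text has no landmark or delayed-entry rule to remove it.

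The trial has no randomized comparator (SAP 2.5), so PFS and OS can be read only against outside data. An inflated supportive OS curve would have no internal control to expose it. A programmer following SAP 12 would produce that curve; one following SAP 4.1.2 would not.

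**Working it through.** **The plan's own figures.** The documents give no survival assumption, so there is no stated figure on this point to reproduce. The only worked design figures are the posterior probabilities in SAP 2.4. With a uniform prior, P(ORR ≥ p | x of n) = P(Bin(n+1, p) ≤ x). For 7/30 and p = 0.15 this gives 91.8% (stated 92%). For 8/20 and p = 0.30 it gives 85.2% (stated 85%). Both reproduce, and neither bears on this point.

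**Inputs from the documents.**
- Cycle length is 21 days (Protocol 8.2). This is the written minimum time to enter the set.
- The first on-treatment scan is at 6 weeks ± 7 days, so day 35 to 49 (Protocol 9.1.2.2). This is the floor only if evaluable means having had that scan.
- One month is 365.25/12 = 30.44 days (SAP 3.2). So 21 days = 0.69 months, 42 days = 1.38 months, and 35 to 49 days = 1.15 to 1.61 months.

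**Assumed.** Median OS in the Treated Set of 4, 6 or 9 months, and the shape of the survival curve.

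**OS, exponential.** With floor t0 and median m, the excluded fraction is 1 − 2^(−t0/m). The conditional median is m + t0, because the exponential is memoryless.

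| Assumed median (months) | Floor 21 days: excluded | Median in set | Floor 42 days: excluded | Median in set |
|---|---|---|---|---|
| 4 | 11% | 4.7 | 21% | 5.4 |
| 6 | 8% | 6.7 | 15% | 7.4 |
| 9 | 5% | 9.7 | 10% | 10.4 |

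With a 6-month median, 6-month OS reads 54% (21-day floor) or 59% (42-day floor) instead of 50%. Across the scan window the gain in the median is 1.15 to 1.61 months.

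**OS, rising hazard.** For a Weibull with shape 1.5 and median 6, the conditional median t solves (t/6)^1.5 = 1 + (t0/6)^1.5.
- t0 = 1.38: (0.23)^1.5 = 0.110, so t = 6 × 1.110^(2/3) = 6.4, a gain of about 0.4 months. Excluded: 1 − 2^(−0.110) = 7%.
- t0 = 0.69: (0.115)^1.5 = 0.039, so t = 6 × 1.039^(2/3) = 6.15, a gain of about 0.15 months. Excluded: about 3%.

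**PFS at day 90.** This was simulated with 20,000 subjects, scans every 42 days, an assumed latent progression median of 2.5 months, and set entry requiring survival to the first scan.

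| Assumed median OS (months) | Treated Set, early deaths as events | Treated Set, early deaths censored at first dose | Tumor Evaluable Set |
|---|---|---|---|
| 4 | 0.28 | 0.35 | 0.35 |
| 6 | 0.33 | 0.38 | 0.38 |
| 9 | 0.37 | 0.41 | 0.41 |

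The last two columns agree because a subject censored at first dose adds neither an event nor time at risk. Both columns equal the first divided by the fraction reaching the first scan. In the middle row 14.5% die before it, and 0.326/0.855 = 0.38.

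**The case against.** The strongest reply is that the plan already limits this set. SAP 4.1.2 and Protocol 11.2 confine it to response-related summaries, OS is not response data, and the SAP 12 sentence goes on to speak of tumor assessment results. That stands to this extent: a reader might infer that the plan has settled on running every efficacy endpoint in the Tumor Evaluable Set, and the documents do not support that. They contradict each other. The reply does not remove the conflict, because SAP 12 points to a section that holds only Kaplan-Meier methods and the synopsis role is not limited to response. The table and figure lists, which might settle it, are not legible in the public copy.

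Four further objections stand in part.
- A reader might infer that members had to reach a post-baseline scan. The text requires one cycle and evaluability; the six-week floor is an inference. Protocol 8.3 and 9.1.2.3 also ask for imaging when treatment stops before progression, so some early failures would be scanned.
- A gain of 1.4 months whatever the true median is a property of the exponential curve and the 42-day floor. Eligibility requires ECOG 0–1 and life expectancy of at least 3 months, which makes a full hazard from day 1 doubtful.
- A reader might infer that Treated Set PFS is free of the bias. Under the literal first-dose censoring rule in SAP 12.2 it is not.
- The consequence is limited. The set is labelled supportive wherever its role is described, and the posterior go/no-go calculation uses ORR.

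**Conclusion.** The concern holds as an internal conflict that, read one way, yields a biased supportive OS curve. OS is the clean case: at least about three weeks of survival are guaranteed by the written one-cycle rule, and about six weeks if evaluability requires the first scan. The upward shift in median OS is 0.7 to 1.4 months under exponential survival, and about 0.15 to 0.4 months under the rising-hazard example. The medians and curve shapes are assumptions, and the size depends on them.

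For PFS and iPFS, a difference between the two sets exists only if deaths before the first scan count as events. Read literally, SAP 12.2 gives the same upward bias in the Treated Set, so changing the analysis set alone would not cure PFS.

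Nothing here touches the primary result: ORR is the primary endpoint, the Treated Set is the primary population, and no formal test is planned. The change should be made, but the trial's main conclusion does not depend on it.

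**What to change.** 1. In SAP 12, Protocol 11.4.2 and the synopsis, state that OS, PFS and iPFS are analysed in the Treated Set only.
2. In the same places, limit the Tumor Evaluable Set to ORR, DCR, iORR, iDCR and tumor-size change, in line with SAP 4.1.2. TTR and DoR, and their iRECIST versions, concern responders and may be shown in either set.
3. In SAP 12.2, with the matching rule in Protocol 11.4.2, state that a death before the first post-baseline scan is a PFS event on the date of death and is not censored at first dose.
4. Define evaluable in SAP 4.1.2 and Protocol 11.2, including whether a post-baseline scan is required.

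The cost is wording changes and fewer tables. No new data are needed.

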### 12.1 Tumor Assessment

Best overall response is the best response recorded from the treatment start date until the earliest of disease progression or last evaluable tumor assessment before events such as start of new anticancer therapy, death, lost to follow-up, etc. Objective response rate (ORR) is defined as the proportion of subjects whose confirmed best overall response is either Complete Response (CR) or Partial Response (PR) according to RECIST version 1.1. Disease control rate (DCR) is defined as the proportion of subjects with confirmed best overall response of CR, PR or SD according to RECIST version 1.1.

The hierarchy used to determine best overall response is CR>PR>SD>PD. [REDACTED]

The progression date is the earliest date among all images of PD lesion. If a subject does not experience PD in one disease assessment, his/her non-PD date will be the latest date among all images of the disease assessment.

Overall best response categories (including: CR, PR, PD, SD), ORR and DCR will be summarized (categorical descriptive analysis), together with the two-sided exact (Clopper-Pearson) 95% confidence intervals.

Based on the cumulative data about ORR along with prior assumption at each stage, posterior probability of ORR  $\geq 15\%$  for cohort 1 and ORR  $\geq 30\%$  for cohort 2 would be computed to determine go/no-go decision of the next stage. This cumulative data analysis will be implemented only if at least one response is observed from stage 1 of each cohort.

According to iRECIST, Best Overall Response (iBOR) of complete response (CR/iCR), partial response (PR/iPR), stable disease (SD/iSD), Progressive disease (iPD) or unevaluable (iUE) will be derived. iORR, iDCR, iTTR, iDoR and iPFS will be analyzed in the same manner as used analyses in accordance with RECIST 1.1. iPD is defined as the time point of first iUPD without subsequent iSD, iPR or iCR before study treatment discontinuation.

For the sum of diameter in target lesion, percent change from baseline at each scheduled tumor assessment time-point and maximal tumor shrinkage from baseline during the study will be summarized.

### 12.2 Time to Event Endpoints (TTR, DoR, PFS and OS)

The time to event endpoints, including time to response (TTR), duration of response (DoR), progression-free survival (PFS) and overall survival (OS) will be summarized descriptively and graphically by the Kaplan-Meier methodology, as described in Section 3.3.

TTR is defined as the time from the date of first administration of study treatment to first documented CR or PR. DoR is measured from the date of the first observation of tumor response (CR or PR, whichever occurs first) to the date of disease progression or death for the subject with an objective response. PFS is defined as the time from the date of first administration of study treatment to determination of tumor progression by RECIST version 1.1 or death due to any cause, whichever occurs first. OS is defined as the duration of time from the treatment start date to time to death from any cause. If subjects survive at the time of analysis, the subject will be censored at the last date of survival confirmed.

TTR, DoR, PFS, and OS will be calculated in days, as well as in months.

For the tumor-related time-to-event endpoints, subjects who have not experience any event (Progressive Disease (PD) or Death) at the time of analysis will be censored at the date of the last evaluable tumor assessment. However, if the subject progresses or dies after two or more consecutive missed assessments

or start of new anticancer therapy, the subject will be censored at the time of the last evaluable assessment prior to starting new anti-cancer therapy/missed assessments. If the subject has no evaluable baseline/post-baseline assessment, subject will be censored at the date of first administration of study treatment. In case of subjects entering the extension part, the data will be treated as censored at the date of the last evaluable tumor assessment on or before the first administration date in the extension part.

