## 2.4 Sample Size

[figure not shown]
There is little known about the objective response rate from the subjects who have progressed on at least 2 prior systemic treatments for advanced or metastatic gastric cancer excluding check point inhibitor (CPI). In addition, considering the study nature to explore the safety and efficacy by FLX475 and pembrolizumab, no formal statistical testing will be done. As stated in the study design part, each cohort will enroll target subjects separately and both cohorts will initiate 2-stage design. The initial number of target subjects for the 1st stage for both cohorts is determined as 10 based on feasibility. However, the target subject number for the 2nd stage would be determined based on the overall safety assessment and the posterior probability of at least 80% to achieve the ORR  $\geq 15\%$  and ORR  $\geq 30\%$  for cohort 1 and cohort 2, respectively.

The posterior probability for ORR  $\geq 15\%$  and ORR  $\geq 30\%$  for cohort 1 and 2, respectively, based on the responses in the first and second stage is described in the Table 11.1:1 and Table 11.1:2 below assuming uniform prior distribution for ORR. For example, if we observed 1 response out of the initial 10 subjects of cohort 1 at 1st stage followed by 6 responses out of additional 20 subjects at 2nd stage, we could assume that the probability of ORR  $\geq 15\%$  by FLX475 and pembrolizumab combination therapy would be 92% based on the observed data (Table 11.1:1). Also, if we observed 1 response out of the initial 10 subjects of cohort 2 at 1st stage followed by 7 responses out of additional 10 subjects at 2nd stage, we could assume that the probability of ORR  $\geq 30\%$  by FLX475 and pembrolizumab combination therapy would be 85% based on the observed data (Table 11.1:2).

[figure not shown]
Considering the minimum posterior probability of 80% to achieve ORR  $\geq 15\%$  for cohort 1 and  $\geq 30\%$  for cohort 2 as well as the overall safety data, the total number of subjects for each cohort will be adjusted after each stage.

- Prior distribution for ORR ( $P$ )  $\sim$  Unif (0,1)
- Observed data  $X \sim$  Binomial ( $N, P$ )
- Posterior distribution for ORR,  $(P| X) \sim$  Beta ( $1+X, 1+N-X$ ).
- **Table 11.1:1 Posterior probability of ORR  $\geq 15\%$  for Cohort 1 by number of subject and response**

[REDACTED]

- **Table 11.1:2 Posterior probability of ORR  $\geq 30\%$  for Cohort 2 by number of subject and response**

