### 3.3 Inferential Analyses

The time to event endpoints will be analyzed using the Kaplan-Meier survival analysis method. The survival functions of the time to event endpoints will be summarized for the 25th percentile, median, and 75th percentile and their 95% confidence intervals.

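### The progression/death event-and-censoring rule in SAP 12.2 also covers time to response, whose event is CR or PR, and the readable text does not limit TTR or iTTR to responders

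*SAP*

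**What the plan says.** - **Event and time origin.** SAP 12.2: "TTR is defined as the time from the date of first administration of study treatment to first documented CR or PR".
- **Method.** SAP 12.2 has TTR, DoR, PFS and OS "summarized descriptively and graphically by the Kaplan-Meier methodology". Protocol 11.4.2 agrees: "Time-to-event endpoints, including TTR, DoR, PFS and OS, will be summarized descriptively and graphically using Kaplan-Meier (KM) methodology". SAP 3.3 asks for time-to-event results to be "summarized for the 25th percentile, median, and 75th percentile and their 95% confidence intervals", and SAP 3.1 adds Kaplan-Meier plots by cohort.
- **Censoring.** The only rule for the tumour-related time-to-event endpoints, in both documents, is that "subjects who have not experience any event (Progressive Disease (PD) or Death) at the time of analysis will be censored" at the last evaluable tumour assessment. The SAP also censors subjects who enter the extension part at their last evaluable assessment on or before the first extension dose. It makes no exception for a response already recorded.
- **Population.** SAP 12: "Efficacy endpoints will be analyzed for the treated set and tumor evaluable set". DoR runs "to the date of disease progression or death for the subject with an objective response". The TTR definition has no such limit.
- **iTTR.** SAP 12.1 handles the iRECIST endpoints in the same way as their RECIST 1.1 counterparts.

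**The concern.** The rule names progression or death as the event, but the TTR event is a response. Applied as written, it censors a responder who has not progressed although the TTR event has occurred. It also gives a progressing non-responder an event without a response date.

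A programmer must therefore choose a rule, and the choices give different results. One choice is to keep all treated subjects and censor non-responders when they progress or at their last scan. Kaplan-Meier then treats them as still able to respond. Under SAP 12.1, best overall response closes at progression, so they cannot. The response curve would then rise above the ORR.

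TTR and iTTR are listed secondary endpoints. At stake are their curves and quartiles, not the primary result.

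**Working it through.** **Figures in the plan.** The documents give no TTR figure. Their only worked results are posterior probabilities from Beta(1+X, 1+N−X) in SAP 2.4. For 7/30, P(ORR ≥ 15%) under Beta(8, 24) is 0.918 (stated 92%). For 8/20, P(ORR ≥ 30%) under Beta(9, 13) is 0.852 (stated 85%). Both reproduce, and neither uses TTR.

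**The literal rule, case by case**

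| Subject | TTR definition | Progression/death rule |
|---|---|---|
| Responder, no progression or death | Event at first CR/PR | Censored at last evaluable scan |
| Non-responder with progression | No event | Event, but no response date |

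**All treated subjects, non-responders censored at progression**

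Inputs from the documents: benchmark ORRs of 15% and 30% (SAP 2.1) and scans every 6 weeks in year 1 (Protocol 9.1.2.2).

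Assumptions, because the documents give no timing:
- First responses fall 55/25/15/5% at weeks 6/12/18/24.
- Non-responders progress 35% at week 6 and 20% at week 12 (pattern A), or 45% and 25% (pattern B).
- The remaining non-responders (45% in A, 30% in B) are followed past week 24.

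Formula: 1 − KM = 1 − Π(1 − d/n), where d is the fraction responding at a visit and n the fraction still at risk. At ORR 15%, pattern A:
- Week 6: d = 0.15 × 0.55 = 0.0825, n = 1.
- Week 12: n = 1 − 0.0825 − 0.85 × 0.35 = 0.62, d = 0.0375.
- Week 18: n = 0.62 − 0.0375 − 0.85 × 0.20 = 0.4125, d = 0.0225.
- Week 24: n = 0.4125 − 0.0225 = 0.39, d = 0.0075.
- Product: 0.9175 × 0.9395 × 0.9455 × 0.9808 = 0.799, so 1 − KM = 0.201.

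| True ORR, pattern | d/n week 6 | d/n week 12 | d/n week 18 | d/n week 24 | 1 − KM |
|---|---|---|---|---|---|
| 15%, A | 0.0825/1 | 0.0375/0.6200 | 0.0225/0.4125 | 0.0075/0.3900 | 0.201 |
| 15%, B | 0.0825/1 | 0.0375/0.5350 | 0.0225/0.2850 | 0.0075/0.2625 | 0.237 |
| 30%, A | 0.165/1 | 0.075/0.590 | 0.045/0.375 | 0.015/0.330 | 0.388 |
| 30%, B | 0.165/1 | 0.075/0.520 | 0.045/0.270 | 0.015/0.225 | 0.444 |

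In each row the true cumulative probability of response is the ORR. The direction is general: a non-responder removed before a later response lowers n, raises d/n and pushes 1 − KM up.

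**A second timing pattern.** Assume responses 60/30/10% at weeks 6/12/18, and exponential times to progression in non-responders with median 8 weeks (cohort 1) or 12 weeks (cohort 2). Over 3,000 simulated trials per setting, the mean final value of 1 − KM was 0.20 at ORR 15% (N = 30) and 0.35 at ORR 30% (N = 20). The direction is the same; the excess at 30% is smaller.

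**The SAP's 8/20 example under three readings.** Assume responses in 5, 2 and 1 subjects at weeks 6, 12 and 18, and non-responders leaving 5, 3, 2 and 2 at weeks 6, 12, 18 and 24.
- Non-responders censored: 1 − (15/20)(8/10)(4/5) = 0.52 against 8/20 = 0.40; median 18 weeks.
- Progression counted as the event: the curve goes to 1.00, although 40% responded.
- Responders only, response as the event: 5/8 by week 6 and 7/8 by week 12, so the quartiles are 6, 6 and 12 weeks, with no distortion.

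**The case against.** The strongest reply is that TTR needs a response date, so a responders-only analysis is the natural reading, and that the progression/death wording was written for PFS and DoR. The general statement in SAP 12 about analysis sets also covers DoR, which is necessarily a responder subset, so it does not by itself fix the TTR denominator. The population columns in SAP 18 and 20 are not readable and may settle the matter. All of this stands: one cannot say that all treated subjects will enter the TTR curve. It does not remove the mismatch, because even in responders the rule as written censors those who have not progressed.

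A reader might infer that the TTR curves and quartiles are bound to be inflated, undefined or not reached. The documents do not support that. Those are outcomes of different readings, and one is not an error: in a correct all-subject analysis with ORR below 25%, all three quartiles are properly reported as not reached.

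A reader might also infer that the report will contradict its own ORR. SAP 3.3 calls for quartiles, not a response probability, and SAP 3.1 puts the product-limit estimates in appendices. An excess would show only there and on a Kaplan-Meier plot, and only if non-responders are censored.

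Finally, "no formal statistical testing will be done" and TTR is descriptive. That stands, and it limits the severity.

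**Conclusion.** The point holds as a mismatch in a stated rule, and it is minor. SAP 12.2 and Protocol 11.4.2 apply a progression/death event to an endpoint whose event is response, and no readable text repairs this or states the TTR population.

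The numerical consequence is conditional. If all treated subjects are analysed and non-responders are censored at progression or last scan, the curve ends about 0.05 to 0.09 too high at a true ORR of 15%, and about 0.09 to 0.14 too high at 30%, under the first timing assumptions. The second pattern gives about 0.05 at both rates. The direction needs only that some non-responders leave before the last response. If TTR is summarised in responders with response as the event, there is no distortion.

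ORR, its Clopper-Pearson interval and the posterior go/no-go rule do not use TTR and are unaffected.

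**What to change.** In SAP 12.2:

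1. Define the TTR event as the first CR or PR of a confirmed response, and the iTTR event as the first iCR or iPR of a confirmed response.
2. Summarise both in confirmed responders: n, median, quartiles and range. Kaplan-Meier is not needed there, because every subject has the event.
3. If a curve in all treated subjects is wanted, use the cumulative incidence of response with progression and death as competing events. It levels off at the observed response rate.
4. Among the tumour-related endpoints, limit the progression/death and extension-entry censoring rules to PFS/iPFS and DoR/iDoR, so that a response recorded before extension entry stays a TTR event.
5. Record the departure from Protocol 11.4.2 in SAP section 15, which at present lists no changes.

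The cost is SAP wording only; no new data are needed.
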